17.2.5 Amended protocol 02 based on Protocol Amendment 02 (25 April 2017)

REASON FOR AMENDMENT:

1. Change in assessments that will not be repeated at end of study/early discontinuation visit

In section(s): 1.1, 1.3

Rationale:

Correction of error in previous section.

2. Dose calculation based on weight in site and home infusion visits

In section(s): 1.1, 1.2, 1.3

Rationale:

Weight change between visits is insignificant, therefore dose calculation using weight from previous site visit is allowed. In home infusion visit, the last weight taken on site will be used.

3. Clarification of time points at which vital signs should be taken

In section(s): 1.1, 1.2, 1.3

Rationale:

Time points added were missing from previous version.

4. Clarification of assessments needed upon manufacturing scale change

In section(s): 1.1, 1.2, 1.3, 1.4, 9.1.5, 9.2.1, 9.2.3, 9.3.8, 9.5, 10.2.1

Rationale:

Upon manufacturing scale change, certain assessments are requested by health authorities. Details were added in this amendment for clarification.

5. Clarification of neurological examination

In section(s): 1.2, 1.3, 9.1.6.2

Rationale:

Clarify that same neurologist to perform neurological examination from any of previous studies through this study and all throughout this study if possible

6. Change in dose stopping (and AESI) criteria

In section(s): 10.5.1.3.4

Rationale:

Correction of errors and clarify level of liver function criteria of dose stopping and AESI.

7. Addition of recommendation on usage of cationic amphiphilic antihistamines in rules on concomitant medications

In section(s): 8.6, 8.6.1

Rationale:

Addition of commonly used medications for clarification.

8. Clarification of IAR definition and treatment

In section(s): 8.6, 8.6.1

Rationale:

Clarify language of IAR description and caution of IAR suggestive of hypersensitivity treatment about medications that may affect study medication efficacy.

9. Clarification of liver biopsy evaluation

In section(s): 9.1.12

Rationale:

Clarification of liver biopsy assessment language

10. Addition of future use of samples section

In section(s): 9.6

Rationale:

Missing from previous version

17.2.6 Amended protocol 01 based on Protocol Amendment 01 (23 March 2016)

REASON FOR AMENDMENT:

Changes listed in this section are regarded as “substantial” because they have a significant impact on:

- The safety or physical or mental integrity of the patients,
- The scientific values of the trial; or,
- The conduct or management of the trial.

1. Change expected number of patients from “65-70 patients” to “up to 17 patients.”

In sections: Clinical trial summary (Study population, Total expected number of patients), 6.

Rationale: This trial allows current patients to continue treatment. Based on the number of patients in this trial and the DFI13803 pediatric trial, the maximum number of patients is already known to be 17.

2. Provide option for home infusions.

In sections: Clinical trial summary (Dose regimen), 8.1.1, 10.2.

Rationale: Patients are on stable doses that they have been tolerating well. This provision eases the travel and hospitalization burden on patients without affecting patient safety.

3. Provide specific guidelines on treatment “reintroduction” defined as management of patients who have missed 1 or more olipudase alfa doses.

In sections: Clinical trial summary (Dose regimen), 8.1.1, 8.1.5.

Rationale: Issue was not addressed in previous version.

4. Remove the requirement that the sponsor must be consulted to determine the appropriate dose of olipudase alfa for dose adjustments or if a patient misses 1 or more doses.

In section: Clinical trial summary (Dose regimen), 8.1.1, 8.1.4.

Rationale: Guidance on how to restart treatment when patients have missed consecutive doses is provided in Section 8.1.1 of the protocol.

5. Remove continuous heart rate monitoring as an endpoint.

In sections: Clinical trial summary (Endpoints, Primary endpoints, Data pertaining to the safety and tolerability of olipudase alfa), 1.1, 9.1.1, 9.2.

Rationale: Patients in the LTS13632 trial have all completed the dose escalation regimen. As such, they are outside the period where fluctuations of ceramide could lead to more severe adverse events. The results of continuous ECG monitoring to date from studies DFI13412 and LTS13412 have not revealed any clinically significant changes. Moreover, enzyme therapies, as a class effect, are not known to detrimentally effect cardiac function. As such, continuous ECG monitoring was removed.

6. Add these endpoints.

In sections: Clinical trial summary (Endpoints, Primary endpoints, Data pertaining to the safety and tolerability of olipudase alfa), 9.1, 9.2.2.1, 9.2.2.2, 9.2.7, 9.2.8, 9.2.9, 9.3, 9.3.7, 9.3.8, 9.3.9, 9.4.2, 9.4.7, 9.4.9.1.

• Primary:

- Extended neurologic examinations in adults and pediatric patients,
- Doppler echocardiography,
- Liver biopsy (original adult patients),
- Liver ultrasound with Doppler (pediatric patients).

• Secondary:

- Hand X-ray for bone age and bone maturation (pediatric patients),
- Tanner staging (pediatric patients),
- Linear patient growth by height Z--score (pediatric patients).

• Other endpoints:

- Cognitive and adaptive function (pediatric patients only, until age 6 years),
- Bone biomarkers,

- **Photographs (optional).**

Rationale: These are relevant clinical endpoints for pediatric patients entering the trial, which were part of the primary pediatric study, and for continued evaluation of adult patients (eg, liver biopsy).

7. **Specify that, “The term ‘pediatric patients only’ means patients coming from the original pediatric trial, DFI13803. Some of these patients will reach adult age [18 years old] while in this study. They will continue the assessments schedule they were on in the original trial. These patients will be adults by age, but they will remain part of the “pediatric patient” cohort.” They will not follow the adult procedures in this study (eg, liver biopsy).**

In sections: Clinical trial summary (Assessment schedule), 1.1, 9, 9.4.9.1.

Rationale: Pediatric patients will not have some baseline assessments for comparison (eg, liver biopsy, DXA of femurs and spine). This statement is intended to clarify to site personnel which assessments pertain to adults and which to pediatric patients.

8. **Add that for patients who missed 3 infusions or more infusions between trials, some assessments may be repeated at study entry after discussion between the sponsor and the investigator.**

In sections: Clinical trial summary (Assessment schedule), 1.1.

Rationale: Since the rate at which sphingomyelin reaccumulates when olipudase alfa is interrupted, it may be necessary to repeat some efficacy assessments in case of prolonged investigational product suspension.

9. **Add: “If a patient has missed 3 or more doses ≥ 0.6 mg/kg, reintroduction of olipudase alfa for patients receiving infusions at home should occur at the hospital/study site. If a patient misses 2 or fewer doses, the investigator can decide whether reintroduction for patients receiving infusions at home should occur at the hospital/study site.”**

In sections: Clinical trial summary (Dose regimen), 1.1, 8.1.1, 8.1.5.

Rationale: To ensure patient’s safety.

10. Add assessments for patients who require dose reintroduction.

- **Patients who require dose reintroduction will have these assessments at each infusion until reaching their usual dose of olipudase alfa:**
 - **Before infusion: vital signs, liver function tests, hematology, ECG, and safety biomarkers,**
 - **Immediately after infusion: vital signs and ECG,**
 - **24 hours: vital signs, liver function tests, and safety biomarkers,**

- **48 hours: vital signs, liver function tests, hematology, ECG, and safety biomarkers.**

In sections: Clinical trial summary (Assessment schedule), 1.1, 8.1.5.

Rationale: To monitor patient safety during reintroduction.

11. Add that PK testing will only occur yearly and upon the introduction of a new manufacturing scale.

In sections: 1.2, 9.4.8.

Rationale: Provide appropriate and continuous monitoring, in particular for manufacturing scale changes.

12. Add that for a new manufacturing scale, if treatment is not interrupted, PK sample collection will take place at the patient's last infusion under the current manufacturing scale and at the first infusion under the new manufacturing scale.

In sections: 1.1, 1.2, 9.4.8.

Rationale: To provide patients' data on drug comparability.

13. Add that if a manufacturing scale change occurs, immune response assessments will be monthly for the first 6 months after starting the new scale, and quarterly after that.

In sections: 1.1, 1.2, 9.4.8.

Rationale: Per FDA request.

14. Add that in case reintroduction of olipudase alfa coincides with a manufacturing scale change, PK samples will be collected at the infusion at which patients receive their usual dose of olipudase alfa under the new manufacturing scale.

In sections: 1.2, 9.3.8.

Rationale: To provide patients' data on drug comparability.

15. Added PK sampling times, number of samples, and parameters in adults and pediatric patients.

In sections: 1.2, 9.3.8.3.

Rationale: Clarify the number of samples for adults and pediatric patients and when they will be obtained.

16. Added PK sampling time point at 96 hours for adults and pediatric patients.

In section: 1.2.

Rationale: Allow comparison of PK in adults and pediatric patients.

17. Added PK total blood volumes for pediatric patients.

In sections: 1.2, 9.5.

Rationale: Specify maximum blood volume for blood samples per health authority requirement.

18. Add that the patients must be willing and able to avoid certain medications and herbal supplements for 10 days before and 3 days after liver biopsies.

In sections: 7.2.1, 8.6.

Rationale: Decrease the risk of bleeding from liver biopsies and to avoid liver toxicity.

19. Clarify patient stopping criteria.

In section: 8.1.7

Rationale: The role of the DMC in an emergency is to review safety data and recommend stopping the study if necessary to ensure patient safety. However, this does not limit the ability of investigators to make an immediate decision to discontinue dosing in an individual patient due to any AE that raises significant concern regarding the safety of olipudase alfa, as described in Section 8.1.6 of the protocol.

20. Remove O₂ saturation from vital signs.

In section: 9.2.4.

Rationale: As part of this amendment to the protocol, dose escalation is not part of the trial. Patients are on stable doses, and therefore monitoring without measuring O₂ saturation is appropriate.

21. Change safety biomarker test from multiplex immunoassay to specific biomarkers including, but not limited to, hsCRP, iron, ferritin, cardiac troponin I, IL-6, IL-8, plasma ceramide and calcitonin.

In sections: 9.2.5, 9.2.10.

Rationale: Given current knowledge about the study drug, broad immunoassay can be replaced by targeted testing.

22. Change the definition of overdose from “at least twice the intended dose within the intended therapeutic interval” to “an increase of at least 30% of the dose to be administered in the specified duration, or if the dose is administered in less than half the recommended duration of administration.”

In section: 10.5.2.3.1.

Rationale: To align with the investigator brochure and the Sanofi template

Signature Page for VV-CLIN-0166491 v10.0
lts13632-16-1-1-amended-protocol07

Approve & eSign

Approve & eSign

## LIST OF ABBREVIATIONS AND DEFINITION OF TERMS

ABAS-3:	Adaptive Behavior Assessment System, Third Edition
ADA:	anti-drug antibody
AESI:	adverse events of special interest
AP:	alkaline phosphatase
AUC 0-inf :	area under the concentration versus time curve from time 0 to infinity
BMI:	body mass index
CL:	total body clearance
C max :	maximum plasma concentration
CV:	coefficient of variation
DBP:	diastolic blood pressure
DBS:	dried blood spots
DP-3:	Developmental Profile 3
DXA:	dual-energy X-ray absorption
ECG:	electrocardiogram
e-CRF:	electronic case report form
FEV 1 :	forced expiratory volume in the first 1 second
FVC:	forced vital capacity
HDL:	high-density lipoprotein
HR:	heart rate
LDL:	low-density lipoprotein
LLOQ:	lower limit of quantification
NE:	not evaluable
PCSA:	potentially clinically significant abnormality
PKDM:	pharmacokinetics, dynamics and metabolism
PT:	preferred term
SAE:	serious adverse event
SAP:	statistical analysis plan
SBP:	systolic blood pressure
SD:	standard deviation
SEM:	standard error of the mean
SMPD1:	acid sphingomyelinase gene
SOC:	system organ class
t 1/2z :	terminal half-life
t max :	time to reach C max
ULN:	upper limit of normal
VAS:	visual analogue scale
VLDL:	very low-density lipoprotein
V ss :	volume of distribution at steady state.
WHO-DRUG:	World Health Organization-Drug Dictionary
WMW:	Wilcoxon-Mann-Whitney

## **1 OVERVIEW AND INVESTIGATIONAL PLAN**

This statistical analysis plan (SAP) provides a comprehensive and detailed description of strategy and statistical techniques to be used to analyze data from the study LTS13632 which is an extension study in the use of olipudase alfa in patients with acid sphingomyelinase deficiency (ASMD). It is based on Amended Clinical Trial Protocol 4, dated 31Jul2019. The purpose of the SAP is to ensure the credibility of the study findings by pre-specifying the statistical approaches to the analysis of study data prior to database lock.

### **1.1 STUDY DESIGN AND RANDOMIZATION**

This is a multinational, multicenter, nonrandomized, open-label, long-term treatment study of approximately 25 patients who have previously participated in a study of olipudase alfa. 5 adult patients rolled over from study DFI13412 into LT13632 study and approximately 20 pediatric patients are expected to roll over from study DFI13803. Patients will be enrolled directly into this study from their previous study. Enrolled patients will receive an IV infusion of olipudase alfa every 2 weeks for 9 years, or marketing approval, whichever comes first. If marketing approval was not available, extension of follow up beyond 9 years would be considered with sponsor's approval.

### **1.2 OBJECTIVES**

#### **1.2.1 Primary objectives**

The primary objective of this study is to obtain data regarding the safety of olipudase alfa in patients with ASMD who are exposed to long-term treatment with olipudase alfa.

#### **1.2.2 Secondary objectives**

The secondary objectives of this study are to obtain data regarding the efficacy of olipudase alfa and to characterize olipudase alfa PD and PK following long-term administration.

### **1.3 DETERMINATION OF SAMPLE SIZE**

Sample size is determined by the number of patients who complete the treatment phase of a previous clinical study of olipudase alfa, sign the informed consent form, and meet the eligibility criteria. The sample size is expected to be 17 – 5 from the adult study, 12 from the pediatric study.

## 1.4 STUDY PLAN

After completion of treatment period in the previous study, patients or their parents/legal guardians (pediatric patients) will sign informed consent to continue treatment in this extension study, at the dose the patient completed the previous study. Patients are expected to transition to the long term study without treatment interruptions. Circumstances where there may be a gap between trials are foreseen in the protocol and treatment administration guidance is provided accordingly (for details, see the protocol). During the treatment period, patients will receive an IV infusion of olipudase alfa every 2 weeks for 9 years (or marketing approval, whichever comes first). If marketing approval was not available, extension of follow up beyond 9 years would be considered with sponsor's approval. Safety and efficacy assessments will occur at regular 3, 6, or 12 month intervals throughout the treatment period. Pharmacodynamic evaluations will occur every 3 months and PK evaluations will occur every 12 months. After treatment completion or premature withdrawal, an end-of treatment visit is scheduled in 2 weeks, and a safety follow-up phone call is scheduled in 30-37 days.

## 1.5 MODIFICATIONS TO THE STATISTICAL SECTION OF THE PROTOCOL

In the section of statistical consideration of the Amended Clinical Trial Protocol 4 Section 11.6.3, treatment period is defined as time from first dose to the last dose of IMP +14 days. In this SAP, in order to incorporate the data from original study (ie, adult study DFI13412 or pediatric study DFI13803), the treatment period definition is changed to “the time from the first infusion of IMP (included) from original study to the end of the current study”.

## 1.6 STATISTICAL MODIFICATIONS MADE IN THE STATISTICAL ANALYSIS PLAN

The SAP Version 2 was based on Amended Clinical Trial Protocol 1. This SAP is based on Amended Clinical Trial Protocol 4 (dated 31July 2019).

- The post-treatment period has been removed from [Section 2.1.3](#), since there is no pre-specified post-treatment period in the protocol.
- The paired t-test was used for testing change from baseline and/or percent change from baseline. Because the baseline value is highly correlated with change from baseline and/or percent change from baseline, the paired t-test has been changed to analysis of covariance with baseline included as covariates as indicated in [Section 2.4.8](#).
- The definition of common TEAE, TEAE of infection, Hypersensitivity IARs and TEAE of bleeding are updated in [Section 2.1.3.1](#).
- Analyses of adverse events by place of infusion was added to this SAP in [Section 2.4.7.1.6](#).
- Subgroup analyses for efficacy endpoints was added to this SAP for patients from DFI13803 in [Section 2.4.8.15](#).
- Patient narratives as described in [Section 2.5](#) will be created, to replace various data listings.

- For Physician's global assessment of change, the 7 categories will be converted to numeric values and summarized, as described in [Section 2.4.8.6](#).

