## **2.4 STATISTICAL METHODS**

Data collected in this study will be presented using summary tables, figures, and data listings. Descriptive statistics for categorical variables will be provided using frequencies (n) and percentages (%). Descriptive statistics for continuous variables will be provided using number of observations (n), mean, standard deviation (SD), median, minimum, and maximum. All data used in tabular summaries or figures will be supported by listings of underlying data – raw and/or derived, and all figures will be supported by relevant summary information.

All summaries will be provided for the LTS population, along with separate subgroups in the population according to which original study the patient belonged to: DFI13412 (adult study, Phase 1B, 26 weeks, 5 patients), DFI13803 (pediatric study, Phase 1/2, 64 weeks, 12 patients). In addition, similar summaries will be produced by age cohort of adolescent, child, infant for the patients who transition from pediatric study DFI13803.

The scheduled visits in statistical displays will be labelled in months of total follow up time from the first infusion in the original study. For example, a 6-month visit in this study for a patient transitioning from the 26-week DFI13412 study will be identified as Month 12 exposure in the displays. The schedule of measurements for this study will be followed for display presentation with baseline derived from the original study. For patients in this study, the results from the original study visits will be included, unless specified otherwise, for the purpose of understanding the continuity of treatment effect during this extension phase; for details and descriptions of all results from the original study, please refer to the original study CSR. For parameters that are not collected in the extension phase will not be part of this SAP.

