#### **2.4.8.1 *Spleen and liver volumes***

For timing of MRI measuring spleen and liver volume, and the formula for calculating the volumes in multiples of normal (MN), refer to [Section 2.1.4.1](#).

Change from baseline and percent change from baseline for both  $\text{cm}^3$  and MN units, in addition to observed values, will be calculated and summarized for all scheduled visits. The analysis of covariance method (including baseline as covariate) and Wilcoxon-Mann-Whitney (WMW) test p-values (and 95% confidence interval) for the change from baseline and percent change from baseline will be provided in the summary tables for spleen/liver volumes in MN unit. Box plots of observed values for spleen and liver volumes in MN unit will be provided.

The correlation between spleen and liver volumes with other efficacy/safety/pharmacodynamic parameters may be explored graphically.

Analysis of covariance will be used to explore difference among different age cohorts for patients from pediatric study DFI13803, using the following model:

Percent change from baseline = age cohort + baseline

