#### **2.4.8.2 *Pulmonary function testing***

The parameters evaluated are DLco (mL/min/mmHg), FVC (L), FEV1(L), TLC (L). Since the local sites use different equations to calculate percent predicted values, the calculation is standardized internally by using the formula provided in [Section 2.1.4.2](#); the percent predicted values calculated at site will remain in the database but will neither be listed nor summarized. The observed values used in analyses are provided by local sites for original study, and will be used for calculation of percent predicted values. The patients transitioning from the pediatric study will continue to use children formula used during the original study even if the age limit prescribed for that formula is crossed during the extension phase.

For all 4 tests, percent (%) predicted values will be summarized for observed values, change from baseline and percent change from baseline using the safety population at scheduled study visit. The analysis of covariance method (including baseline as covariate) and WMW test p-values for the change from baseline and percent change from baseline will be provided in the summary tables for all 4 tests. Box plots of observed values, percent change from baseline for these 4 tests will be provided for the safety population. By-patient plots for all 4 tests over time will be provided.

Analysis of covariance will be used to explore difference among different age cohorts for patients from pediatric study DFI13803, using the following model:

Percent change in percent predicted PFT from baseline = age cohort + baseline percent predicted PFT

For patients from adult study DFI13412, a binary measure of responder (yes vs no) will be derived based on the change from baseline in % predicted DLco at each post-baseline visit. A patient is a responder at the visit, if the patient has change from baseline in % predicted DLco  $\geq 15$ . This binary measure of % predicted DLco will be included in data listing.

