#### **2.4.8.6 Physician's global assessment of change**

Frequency shift table for physician's global assessment of disease severity (mild, moderate, severe) from the baseline will be provided at each scheduled post-baseline visit. Frequencies and percentages of patients at each clinical status will be provided at each scheduled post-baseline visit. Seven categories of Clinical Status in Physician's global assessment of change as detailed in [Section 2.1.4.6](#) will be converted to numeric values as follows:

- “Marked improvement of daily activities” = 3.
- “Moderate improvement of daily activities” = 2.
- “Mild improvement of daily activities” = 1.
- “No change” = 0.
- “Mild worsening of daily activities” = -1.
- “Moderate worsening of daily activities” = -2.
- “Marked worsening of daily activities” = -3.

Observed numeric values at each post-baseline visits will be analyzed using analysis of covariance (ANCOVA) model with baseline as covariate. The baseline value will be Physician's global assessment of disease severity at screening with value of 1=mild, 2=moderate, 3=severe.

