#### **2.4.8.12 Bone age by hand X-ray (Patients from pediatric study DFI13803)**

For each patient at each scheduled baseline and post-baseline visits, the difference between the bone age and actual age at that visit will be calculated. Then the change from baseline in the bone age and actual age difference will be analyzed with analysis of covariance (ANCOVA) model with baseline bone age and actual age difference as covariate.

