#### **2.4.8.14 Height z-score (Patients from pediatric study DFI13803)**

The height z-score categories will be summarized for all scheduled visits. Change from baseline in height z-score will be analyzed with analysis of covariance (ANCOVA) model with baseline height z-score as covariate.

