#### **2.4.8.15 Subgroup analyses for efficacy (Patients from pediatric study DFI13803)**

For Patients from pediatric study DFI13803, below subgroup analyses will be performed.

To assess persistence of efficacy in patients with different baseline disease severity, the following subgroup analysis will be conducted:

- Spleen volume (MN) by baseline spleen volume severity (severe vs not severe). Severe patients is defined as baseline spleen volume  $>15$  multiple of normal (MN).
- % predicted DLco by baseline % predicted DLco severity (severe vs not severe). Severe patients is defined by baseline % predicted DLco  $<40\%$ .

To assess the impact of immunogenicity on efficacy, descriptive summaries for spleen volume and platelet count will be conducted for the following two groups of patients treated with olipudase alfa:

- Patients with treatment emergent anti-drug antibody (ADA) positive defined as either treatment induced or treatment boosted ADA positive at any time during olipudase alfa treatment.
- Patients with ADA negative defined as neither treatment induced or treatment boosted ADA positive at all time during olipudase alfa treatment.

For all the above subgroup analyses, within each subgroup, the change or percent change from baseline at each longitudinal time point will be summarized and analyzed with the analysis of covariance (ANCOVA) approach with baseline as covariate.

The efficacy measures (spleen volume and platelet count) will also be compared between manufacturing Process B, Process C (█) and Process C (█) as described below.

- To compare Process B and Process C (█), descriptive summaries for above efficacy measures will be created for the patients who started on Process C (█) only (patients never on Process B) versus patients who started on Process B and then switched to Process C (█) (Patients who were ever on Process B). In this analysis, the data when patients were exposed to Process C (█) will be excluded.
- Descriptive summaries for above efficacy measures will be created for the patients who did not switch to Process C (█) yet (patients never on Process C (█)) versus patients who switched to Process C (█) (Patients ever on Process C (█)).
- For patients who switched to Process C(█) and patients who switched to Process C (█) separately, the individual patient plot of observed values at each time point for above efficacy measures will be created with time point for start of each process (B, C (█) and C (█)) added on the plot.

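### The SAP replaces the paired t-test with a baseline-only ANCOVA in a single-arm study without stating what is tested; read as mean change, its standard error is too small

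*SAP*

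**What the plan says.** SAP 1.6 records that "the paired t-test has been changed to analysis of covariance with baseline included as covariates". It gives the strong correlation of baseline with change as the reason and points to section 2.4.8. It also says the paired test had been used to test change and percent change from baseline. The entry sits in a list of changes, but it describes the current method, and later sections apply it:

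- **2.4.8.1, spleen and liver volume (MN):** "The analysis of covariance method (including baseline as covariate) and Wilcoxon-Mann-Whitney (WMW) test p-values (and 95% confidence interval) for the change from baseline".
- **2.4.8.2, four pulmonary function tests:** "The analysis of covariance method (including baseline as covariate) and WMW test p-values for the change from baseline and percent change from baseline".
- **2.4.8.6, physician's global assessment:** "Observed numeric values at each post-baseline visits will be analyzed using analysis of covariance (ANCOVA) model with baseline as covariate". The covariate is screening disease severity scored 1 to 3.
- **2.4.8.12, bone age:** "Then the change from baseline in the bone age and actual age difference will be analyzed with analysis of covariance (ANCOVA) model".
- **2.4.8.14, height z-score:** "Change from baseline in height z-score will be analyzed with analysis of covariance (ANCOVA) model with baseline height z-score as covariate".
- **2.4.8.15, pediatric subgroups:** within each subgroup, change is "summarized and analyzed with the analysis of covariance (ANCOVA) approach with baseline as covariate".

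The general text of 2.4.8 does not mention ANCOVA. No section gives a null hypothesis, the model term tested, the baseline value at which an adjusted mean is evaluated, or the form of its standard error. Protocol 8.2 describes a single-arm, open-label design. The separate models with age cohort plus baseline do contain a group term and are not at issue.

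**The concern.** Adjusting for baseline gains precision when groups are compared, because it removes outcome variation shared across groups. Here there is no group contrast. The adjusted mean is the same number as the raw mean change, and the apparent gain comes from treating the observed mean baseline as known. High correlation, the SAP's reason for the switch, is the condition under which the understatement is largest.

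The results at stake are the ANCOVA p-values for spleen and liver volume and the four lung function tests, and the 95% intervals promised for spleen and liver volume. For global assessment, bone age, height z-score and the subgroups, the SAP names neither p-value nor interval. Any taken from those single-group models would have the same standard-error problem.

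**Working it through.** **Inputs**

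- n = 5 adults and n = 12 children: SAP 2.4, which lists "DFI13803 (pediatric study, Phase 1/2, 64 weeks, 12 patients" beside the five adults. n = 20 children: the approximate count in SAP 1.1.
- Alpha: not stated. Two-sided 5% is assumed, to match the 95% interval in 2.4.8.1.
- r, the correlation of baseline with change: no figure in the documents. |r| = 0 to 0.9 is assumed and shown as a range.
- The plan gives no power, alpha or standard error for this test, so there is no figure to reproduce.

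**Step 1: estimate and standard error.** Fit change = a + b × (baseline − sample mean baseline) + error. The estimate of a is the raw mean change. With r the sample correlation,

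SE(ANCOVA) = SD(change)/√n × √[(1 − r²)(n − 1)/(n − 2)],

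against SD(change)/√n for the paired t-test. In a given data set the ANCOVA value is smaller whenever r² > 1/(n − 1), that is |r| above 0.50 at n = 5, 0.30 at n = 12 and 0.23 at n = 20.

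**Step 2: true error.** With bivariate normal data and zero mean change, the ANCOVA t statistic is distributed as T(n−2)/√(1 − r²), r now being the population correlation. So

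true error = 2 × P[T(n−2) > t(0.975, n−2) × √(1 − r²)].

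Example, n = 12 and |r| = 0.7: t(0.975, 10) = 2.228; √(1 − 0.49) = 0.714; product 1.591; 2 × P[T(10) > 1.591] = 14.3%.

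| n | \|r\| = 0 | 0.3 | 0.5 | 0.7 | 0.9 |
|---|---|---|---|---|---|
| 5 | 5.0% | 5.6% | 7.0% | 10.8% | 25.9% |
| 12 | 5.0% | 5.9% | 8.3% | 14.3% | 35.4% |
| 20 | 5.0% | 6.0% | 8.6% | 15.1% | 37.2% |

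Simulation with 200,000 trials per cell agrees within about 0.2 percentage points. In the same simulations the paired t-test stays at 4.9–5.1%. For pooled samples of 17 and 25, the formula gives 14.9% and 15.3% at |r| = 0.7.

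**Step 3: interval width.** Mean ANCOVA width as a percentage of mean paired width:

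| n | \|r\| = 0.5 | 0.7 | 0.9 |
|---|---|---|---|
| 5 | 97% | 80% | 49% |
| 12 | 88% | 72% | 44% |
| 20 | 87% | 72% | 44% |

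At n = 5 and |r| of 0 or 0.3, the ANCOVA interval is wider than the paired one (112% and 107%), because it loses a degree of freedom.

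**Step 4: the target that makes the ANCOVA right.** If the target is the expected change at the observed mean baseline, held fixed, simulated error is 4.9–5.1%. The model is therefore valid for that target and not for the population mean change.

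**Step 5: other readings.** If a programmer tests the uncentred intercept or the baseline slope instead, the result is not a test of mean change. With zero mean change, n = 12, |r| = 0.7 and an assumed baseline mean of 3 SDs, the intercept is rejected in 75% of runs and the slope in 78%.

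**The case against.** The strongest reply is that the wording already implies an adjusted mean change, because 2.4.8.1 and 2.4.8.2 promise p-values for change from baseline. On that view the ANCOVA is exact once the observed baselines are taken as given. The sample is whoever rolled over from two earlier studies, so a target tied to this cohort can be defended. That stands as a possible target, but the SAP does not adopt it, and the test it replaced addressed mean change.

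The size depends on an assumed correlation. At |r| = 0.3 error is at most 6.0%, and at n = 5 with |r| = 0.5 it is 7.0%. This is correct, and is why a range is shown. The SAP's own description of the correlation points to the upper part of it.

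The figures do not carry over directly everywhere. The global assessment is an ordinal rating with a different covariate. Cutting subgroups at spleen volume above 15 MN or DLco below 40% truncates the baseline range. Lung function is planned only for patients aged at least 5 at original screening, so n may be smaller there. These points limit the numbers but leave the algebra of Step 1 intact.

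The consequences are also bounded. Efficacy is secondary, no decision rule is attached, and the primary safety analysis is descriptive. Protocol 4.1 reports mean falls of 25.3% in spleen volume and 17.1% in liver volume at 6 months in the adult study, so a false positive at zero change is a remote worry for those two endpoints. It matters more for lung function. A reader could rebuild the paired interval from the planned n, mean and SD, but the reported p-values and intervals would remain too optimistic.

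**Conclusion.** The concern holds and should be fixed. The SAP leaves the tested quantity undefined and, read as population mean change, its ANCOVA understates uncertainty. The excess is negligible at r = 0, small at |r| = 0.3 and material from about 0.5. At |r| = 0.7, true error is 10.8% to 15.1% for n = 5 to 20, and intervals are 72% to 80% of their proper width. These figures assume bivariate normal data, evaluation at the sample mean baseline, a two-sided 5% level, and a correlation the documents do not give. The effect is confined to secondary efficacy results.

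**What to change.** - In 2.4.8, state the target: mean change (or percent change) from baseline in the treated population, with the null hypothesis of zero.
- In 2.4.8.1, 2.4.8.2, 2.4.8.12, 2.4.8.14 and 2.4.8.15, use the paired (one-sample) t-test for within-group results, with mean change and its 95% interval.
- In 2.4.8.6, the score is already a rating of change, so test it against 0 with a one-sample method.
- Keep ANCOVA for the models with age cohort plus baseline.
- Delete the rationale in 1.6.

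If the ANCOVA mean is kept, use SE² = s_res²/n + b²s_x²/n, where s_res² is the residual variance, b the slope and s_x² the baseline variance. This gives error of 4.4–4.8% at n = 20 and 4.0–4.5% at n = 12, but 2.4–2.8% at n = 5, where intervals are 118–128% of paired width. It has the same point estimate and a wider interval than the paired t-test at every n, so the paired test is preferable.

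The cost is SAP wording and simpler code, with no new data. Intervals will be somewhat wider where baseline and change are correlated.
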